7.2.5 ADVERSE AND SERIOUS ADVERSE EVENT REPORTING

All serious adverse events must be reported to the IRB according to regulatory requirements. The Principal Investigator will immediately report to the sponsor any serious adverse event, whether or not considered study intervention related, including those listed in the protocol or package insert and must include an assessment of whether there is a reasonable possibility that the study intervention caused the event. Study endpoints that are serious adverse events (e.g., all-cause mortality) must be reported in accordance with the protocol unless there is evidence suggesting a causal relationship between the study intervention and the event (e.g., death from anaphylaxis). In that case, the investigator must immediately report the event to the sponsor.

All serious adverse events (SAEs) will be followed until satisfactory resolution or until the Principal Investigator deems the event to be chronic or the subject is stable. Other supporting documentation of the event may be requested and should be provided as soon as possible.

7.3 UNANTICIPATED PROBLEMS

7.3.1 DEFINITION OF UNANTICIPATED PROBLEMS (UP)

The Office for Human Research Protections (OHRP) considers unanticipated problems involving risks to subjects or others to include, in general, any incident, experience, or outcome that meets all of the following criteria:

- Unexpected in terms of nature, severity, or frequency given (a) the research procedures that are described in the protocol-related documents, such as the Institutional Review Board (IRB)-

approved research protocol and informed consent document; and (b) the characteristics of the subject population being studied;

- Related or possibly related to participation in the research (“possibly related” means there is a reasonable possibility that the incident, experience, or outcome may have been caused by the procedures involved in the research); and
- Suggests that the research places subjects or others at a greater risk of harm (including physical, psychological, economic, or social harm) than was previously known or recognized.

7.3.2 UNANTICIPATED PROBLEM REPORTING

The investigator will report unanticipated problems (UPs) to the reviewing Institutional Review Board (IRB). The UP report will include the following information:

- Protocol identifying information: protocol title and number, PI’s name, and the IRB project number;
- A detailed description of the event, incident, experience, or outcome;
- An explanation of the basis for determining that the event, incident, experience, or outcome represents an UP;
- A description of any changes to the protocol or other corrective actions that have been taken or are proposed in response to the UP.

To satisfy the requirement for prompt reporting, UPs will be reported using the following timeline:

- UPs that are serious adverse events (SAEs) will be reported to the IRB within 10 working days of the investigator becoming aware of the event.
- Any other UP will be reported to the IRB within 10 working days of the investigator becoming aware of the problem.

8 STATISTICAL CONSIDERATIONS

8.1 STATISTICAL HYPOTHESES

- Primary Endpoint(s): The primary aim of this study is to compare the effects of treatment on children’s and mothers’ weight outcomes at 6- and 12-months. Hypothesis 1a: Mothers receiving HABITS will have a lower weight than mothers receiving standard services. Hypothesis 1b: Children receiving HABITS will have slower weight gain than children receiving standard services.
- Secondary Endpoint(s): The secondary aim of this study is to compare the effects of treatment on maternal feeding practices, habit strength of targeted behaviors, and features of the household environment relevant to targeted behaviors at 6- and 12-months. Hypothesis 2: Compared to standard services, HABITS will result in healthier maternal feeding practices (less fried foods and SSB; more vegetables/fruits), greater habit strength of targeted behaviors, and greater home availability of cues that support targeted behaviors

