1 PROTOCOL SUMMARY

1.1 SYNOPSIS

Title:	Leveraging Ongoing Home Visitation Programs to Address Obesity Disparities Among Underserved, Low-Income Mothers and Children (Obesity Health Disparities Research Center)
Study Description:	This two-arm, parallel, randomized controlled trial (RCT) tests the effectiveness of a simple obesity intervention (HABITS) delivered as part of ongoing home visiting services, compared to the existing home visiting services without obesity-related content on mothers' and children's obesity risks.
Objectives:	The objectives of the study are to compare the effects of treatment on children and primary caregivers' weight outcomes at 6 and 12 months, and to compare the effects of treatment on maternal feeding practices, habit strength of targeted behaviors, and features of the household environment relevant to targeted behaviors at 6 and 12 months.
Endpoints:	The primary endpoint is caregiver and child weight at 12-months
Study Population:	Participants will be 148 mothers (>50% African American; 100% low income) and their children (0–5yo at baseline) enrolled in a home visiting program in central Alabama.
Phase:	N/A
Description of Study Intervention:	The HABITS intervention focuses on habit formation and modifications of food and activity cues in the home to support habit formation. Habit formation is focused on improving five behaviors: 1) fruits/vegetables, 2) fried foods, 3) sugar-sweetened beverages, 4) physical activity and 5) self-monitoring.
Study Duration:	12-months
Subject Duration:	12-months

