8.2 SAMPLE SIZE DETERMINATION

The power analysis is prepared for comparing means of weight change from baseline to 12-months between the control and HABITS study arms. A sample size of 59 dyads per group, total of 118 dyads, will have 80% power to detect that mean of weight change in the control is 0.53 standard deviation

apart from that in HABITS by performing two-sided t-test of equal means at $\alpha=0.05$. Since participants will be nested in 18 home visitors, the unadjusted calculated sample size must be further increased by an inflation factor to account for clustering due to home visitors. The inflation factor is given by the following equation: $IF = [1 + (m - 1) p]$, where m represents the number of participants per home visitor, and p represents the intraclass correlation coefficient (ICC), the ratio of between-home visitors and total variability. In this study, we assume ICC is 0.01 consistent with typical values of ICC in community-based studies.⁸⁶ By considering a 15% attrition rate between baseline and 12-month follow-up, the required total sample size is 140 (70 dyads per group). If ICC is weaker or attrition rate is smaller than we expected, we will have stronger power to detect the same difference of means.

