8.3.2 ANALYSIS OF THE PRIMARY ENDPOINT(S)

For the primary endpoints, weight of mother or child between baseline and the 6-month and 12-month timepoints will be calculated and summarized by tabulating and plotting descriptive statistics by the study arms. Linear association of HABITS with weight changes will be estimated and adjusted for demographic

information and other measured covariates by performing mixed regression models with home visitors as a random effect.

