9.2 ABBREVIATIONS

AE	Adverse Event
ANCOVA	Analysis of Covariance
CFR	Code of Federal Regulations
CONSORT	Consolidated Standards of Reporting Trials
DHHS	Department of Health and Human Services
GCP	Good Clinical Practice
HIPAA	Health Insurance Portability and Accountability Act
ICH	International Conference on Harmonisation
ICMJE	International Committee of Medical Journal Editors
IRB	Institutional Review Board
LSMEANS	Least-squares Means
NCT	National Clinical Trial
NIH	National Institutes of Health
OHRP	Office for Human Research Protections
PI	Principal Investigator
QA	Quality Assurance
QC	Quality Control
SAE	Serious Adverse Event
SAP	Statistical Analysis Plan
SOA	Schedule of Activities
SOP	Standard Operating Procedure
SSB	Sugar-Sweetened Beverage
UP	Unanticipated Problem
US	United States

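### Caregiver primary outcome is worded as 12-month weight but powered and modelled as weight change, and baseline weight is not named as a covariate

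*Combined protocol and SAP*

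**What the plan says.** The caregiver outcome appears in two forms.

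- **As a level.** The synopsis (1.1) states: "The primary endpoint is caregiver and child weight at 12-months". Hypothesis 1a (8.1) states: "Mothers receiving HABITS will have a lower weight than mothers receiving standard services". The child hypothesis beside it is worded as change: "Children receiving HABITS will have slower weight gain than children receiving standard services".
- **As change.** Section 8.2 states: "The power analysis is prepared for comparing means of weight change from baseline to 12-months between the control and HABITS study arms". Section 8.3.2 states: "Linear association of HABITS with weight changes will be estimated and adjusted for demographic" and other covariates, in a mixed model with home visitor as a random effect. Section 8.3 assigns this same model to Hypothesis 1.

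Sections 8.3, 8.3.1 and 8.3.2 describe the adjustment set only as demographics plus further measured variables. Baseline weight is not named, although section 7.1 has it measured in duplicate at Visit 1. The abbreviation list (9.2) includes "Analysis of Covariance", but section 8 does not use the term.

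**The concern.** Without baseline weight in the model, level and change are different estimators. Under randomisation they target the same expected arm difference, but in one trial they can diverge if the arms differ in weight at the start. A reader who holds the trial to its endpoint row would look for a difference in 12-month weight. A reader who follows section 8.3.2 would look for a difference in change.

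The two also differ in precision, because women's weights usually vary far more between women than within a woman over a year. A power figure calculated for one cannot be read across to the other. Leaving the covariates open also means that the decision to adjust for baseline weight could be taken after the data are seen.

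This point concerns caregiver weight only.

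**Working it through.** **Inputs from section 8.2:** 59 per group, a difference of 0.53 SD of weight change, two-sided t-test at 0.05, 18 home visitors, ICC 0.01, 15% attrition, 140 dyads in total.

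**Assumptions, not in the documents:** equal SD of weight at baseline and 12 months, and a baseline-to-12-month correlation r. A wide range of r is shown. High values are plausible for adult weight. However, mothers who become pregnant stay in the study (2.3.1), and weight loss related to childbirth is not an exclusion (4.2); both could lower r.

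**1. The plan's own figure.** The noncentrality is 0.53 × √(59/2) = 2.88 on 116 df, which gives power of 81.5%. The stated 80% reproduces for change. At the planned enrolment:
- retained per group: 70 × 0.85 = 59.5
- dyads per visitor: 119/18 = 6.61
- inflation factor: 1 + 5.61 × 0.01 = 1.056
- effective number per group: 59.5/1.056 = 56.3
- power for change, t-test on the effective number: 79.6%

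**2. Level and change coincide once baseline is in the model.** Let Y0 and Y1 be baseline and 12-month weight and T the arm. If Y1 = a + bT + cY0 + visitor effect + error, then Y1 − Y0 = a + bT + (c − 1)Y0 + the same visitor effect and error. The arm coefficient b and its standard error are identical; only the coefficient of Y0 changes.

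**3. Power of each contrast for the same difference in kg** (59 per group, ignoring clustering). The SD of change is √(2(1 − r)) times the SD of weight. The standardised differences are therefore:
- change: 0.53 at any r
- 12-month weight adjusted for baseline: 0.53 × √(2/(1 + r))
- unadjusted 12-month weight: 0.53 × √(2(1 − r))

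| r (assumed) | Change, as planned | Adjusted for baseline: d, power | Unadjusted 12-month weight (not specified as primary): d, power |
|---|---|---|---|
| 0.50 | 81.5% | 0.612, 91% | 0.530, 81.5% |
| 0.70 | 81.5% | 0.575, 87% | 0.411, 60% |
| 0.80 | 81.5% | 0.559, 85% | 0.335, 44% |
| 0.90 | 81.5% | 0.544, 83% | 0.237, 25% |
| 0.95 | 81.5% | 0.537, 82% | 0.168, 15% |

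The residual variance of the adjusted contrast is (1 + r)/2 times that of change, which is never above 1. Under these assumptions the change calculation is therefore conservative for the adjusted contrast.

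**4. Effect of chance baseline imbalance.** In units of the SD of weight, the standard error of the baseline arm difference is √(2 × 1.056/59) = 0.189. Given an imbalance D, unadjusted level carries rD, change carries (1 − r)D in the opposite direction, and the adjusted contrast carries essentially none. For one standard error of imbalance:
- r = 0.95: change is shifted by 0.05 × 0.189 = 0.009, against a target of 0.168
- r = 0.90: change is shifted by 0.10 × 0.189 = 0.019, against a target of 0.237
- unadjusted level is shifted by 0.180 (r = 0.95) or 0.170 (r = 0.90), about the size of the target effect or somewhat below it

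**The case against.** The strongest reply is that the plan is consistent where it counts. Section 8.2 powers change, section 8.3 assigns the change model to Hypothesis 1, and section 8.3.2 repeats it for the primary endpoints. Hypothesis 1a can be read as giving a direction, and under randomisation the expected arm difference in change equals that in 12-month weight. The change model can therefore test it. All of this stands.

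A reader might infer from the endpoint wording that the true power is 15% to 25% (r = 0.95 to 0.90). The documents do not support that. No section makes an unadjusted comparison of 12-month weights the primary analysis. In section 8.3.1 the reference to each measurement time opens the sentence on descriptive statistics, not the later t-test sentence. The t-test sentence does not say whether level or change is compared, and the section then assigns primary outcomes to mixed models. Those power figures also rest on a correlation that the plan does not state.

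It is also fair to say that leaving out the baseline term costs little if change is analysed: 81.5% against 82% to 83% at high r, with 5% to 10% of any imbalance carried over. Clustering adds little to the imbalance, since its standard error is √(2/59) = 0.184 without it and 0.189 with it. The open covariate description could cover baseline weight, and an unused abbreviation is weak evidence of intent. Aligning all sections to change would also remove the contradiction.

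What the reply does not remove is that the endpoint row and Hypothesis 1a still differ from sections 8.2 and 8.3.2, and that baseline weight, though it could be included, is not committed to.

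**Conclusion.** The mismatch in wording and the unnamed covariate are real. A power shortfall is not shown: 80% is correct for the planned change analysis (81.5% with 59 per group, ignoring clustering). That figure would not apply to an unadjusted comparison of 12-month weights, and the plan does not specify that test as primary.

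Pre-specifying baseline weight is a free improvement. It gives one arm estimate whichever wording is used, removes the dependence on chance baseline imbalance, and keeps or raises power. The gain is modest: about 82% at r = 0.95, 83% at 0.90, 85% at 0.80 and 91% at 0.50, against 81.5% for raw change. These figures assume equal SDs at the two visits and a correlation that the documents do not give.

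**What to change.** - **1.1, 8.1 and 8.3.2:** define the caregiver primary contrast as the arm difference in 12-month weight, adjusted for the caregiver's own baseline weight.
- **8.3.2 (and the matching text in 8.3):** name baseline weight as a fixed covariate in the planned home-visitor mixed model, and report the adjusted arm difference with a 95% confidence interval. Note that the estimate is the same whether the response is entered as level or change.
- **8.3.1 and 8.3.2:** label unadjusted weights by arm at each visit as descriptive.
- **8.2:** state that the 80% refers to the change contrast, which is conservative for the baseline-adjusted one.

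The cost is wording and one degree of freedom. No new data are needed and the sample size does not change.

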8.2 SAMPLE SIZE DETERMINATION

The power analysis is prepared for comparing means of weight change from baseline to 12-months between the control and HABITS study arms. A sample size of 59 dyads per group, total of 118 dyads, will have 80% power to detect that mean of weight change in the control is 0.53 standard deviation

apart from that in HABITS by performing two-sided t-test of equal means at $\alpha=0.05$. Since participants will be nested in 18 home visitors, the unadjusted calculated sample size must be further increased by an inflation factor to account for clustering due to home visitors. The inflation factor is given by the following equation: $IF = [1 + (m - 1) p]$, where m represents the number of participants per home visitor, and p represents the intraclass correlation coefficient (ICC), the ratio of between-home visitors and total variability. In this study, we assume ICC is 0.01 consistent with typical values of ICC in community-based studies.⁸⁶ By considering a 15% attrition rate between baseline and 12-month follow-up, the required total sample size is 140 (70 dyads per group). If ICC is weaker or attrition rate is smaller than we expected, we will have stronger power to detect the same difference of means.

8.3 STATISTICAL ANALYSES

At each time of measurement, descriptive statistics and measures of association will be used to summarize demographic characteristics and outcome measures. The analysis will also include graphical and statistical analysis of outlying observations and distributional characteristics of variables. Differences in outcomes of interest between the control and HABITS will be assessed by t-test of equal means and Chi-square test of equal proportions for continuous, ordinal, and categorical values, respectively.

For hypothesis 1 (primary outcomes), weight of mother or child between baseline and the 6-month and 12-month timepoints will be calculated and summarized by tabulating and plotting descriptive statistics by the study arms. Linear association of HABITS with weight changes will be estimated and adjusted for demographic information and other measured covariates by performing mixed regression models with home visitors as a random effect.

For hypothesis 2 (secondary outcomes), the analyses approach planned for Aim 1 will be used for determining if HABITS is associated with changes in maternal feeding practices, habit strength of targeted behaviors, or the household environments between baseline and 6- or 12-month follow-up.

Missing data will be addressed using multiple imputation and/or full information maximum likelihood estimation. Psychometric properties of the study scales will be investigated to ascertain appropriate validity and reliability. All statistical analyses will be performed using the most current version of SAS 9.4. Final results will be determined to be statistically significant when the accompanying statistical test yields a two-tailed probability of 0.05 or less.

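### The plan does not rank 6 and 12 months as primary times in 8.1 and 8.3.2, lets unclustered tests assess outcomes at 0.05, and gives no success rule for the mother and child hypotheses

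*Combined protocol and SAP*

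**What the plan says.** **Primary time.** The synopsis endpoint row states: "The primary endpoint is caregiver and child weight at 12-months". Section 8.2 agrees: "The power analysis is prepared for comparing means of weight change from baseline to 12-months between the control and HABITS study arms". Section 3.2 dates primary completion by the last 12-month assessment. The synopsis objectives row, however, refers to "weight outcomes at 6 and 12 months", and 8.1, under its primary-endpoint bullet, to "weight outcomes at 6- and 12-months". Sections 8.3 and 8.3.2 also take both times together for the primary outcomes, with no ranking.

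**Primary hypotheses.** Section 8.1 lists two: "Hypothesis 1a: Mothers receiving HABITS will have a lower weight than mothers receiving standard services" and "Hypothesis 1b: Children receiving HABITS will have slower weight gain than children receiving standard services". Section 8.2 sizes one comparison at 0.05 and does not say whose weight it concerns.

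**Decision rule.** The only one is in 8.3: "Final results will be determined to be statistically significant when the accompanying statistical test yields a two-tailed probability of 0.05 or less".

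**Tests.** Section 5.2 randomises home visitors. Section 8.3.1 assigns primary and secondary outcomes to mixed models with home visitor as a random effect, and 8.3.2 and 8.3.3 follow it. Sections 8.3 and 8.3.1 also say that differences in outcomes of interest are assessed by t-test and chi-square, and 8.3.4 compares adverse events between arms by chi-square. None of these tests is called descriptive.

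**The concern.** Three choices that should be settled before the data are seen are left open or stated in two ways.

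- **Time.** With 6 and 12 months both under the primary endpoints, a 6-month result could be reported as primary although the trial is sized for 12 months.
- **Test.** Two kinds of test are said to assess outcomes, under one significance rule. If they disagree, the text has no explicit statement that the clustered one decides.
- **Success.** A result positive for the mother only, or for the child only, could be called success or failure afterwards. Section 9.1.2 also lists the primary endpoint having been met among the reasons for ending the study, and that cannot be judged without a rule.

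At stake is whether the 5% error rate and 80% power in 8.2 describe the conclusion the trial will draw.

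**Working it through.** **Inputs from the documents.** Two-sided alpha 0.05 (8.2, 8.3); 0.53 SD, 59 dyads per group, 80% power, ICC 0.01, 15% attrition and total 140 (8.2); total 148 from the synopsis ("Participants will be 148 mothers"); 18 home visitors, 9 per arm (3.1, 5.2). The two totals differ, so results are given for both.

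**Assumptions, not in the documents.** Mother–child correlation of 0 to 0.5; an ICC of 0.05 as a stress value; 0.53 SD on both outcomes where joint power is shown.

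**1. The plan's own figure.** A two-sample t-test at 0.53 SD, two-sided 0.05 and 80% power needs 57 per group. With 59 per group power is 81.5%. The stated figure is reproduced closely, for a single comparison at the full 0.05.

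**2. Primary time.** For 12 months alone: the synopsis endpoint row, 3.2 and 8.2. For 6 and 12 months unranked: the synopsis objectives row, 8.1, 8.3 and 8.3.2. The sentence that defines the endpoint is in the first group, so the second should be brought into line with it.

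**3. A t-test that ignores visitors.** Inflation factor IF = 1 + (m − 1) × ICC; approximate type I error = 2 × [1 − Φ(1.96/√IF)].
- m = 7, ICC 0.01: IF = 1.06, 1.96/√1.06 = 1.904, error 5.7%.
- m = 6.61 (119 completers), ICC 0.01: IF = 1.056, error 5.6%. Simulation checks of the ICC 0.01 case gave about 5.5–5.7%.
- m = 7, assumed ICC 0.05: IF = 1.30, 1.96/√1.30 = 1.719, error 8.6%.

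**4. Two 12-month tests at 0.05, success on either.** Independent: 1 − 0.95² = 0.0975. Bivariate normal: 0.0951 at correlation 0.3 and 0.0907 at 0.5. If both must succeed, the error rate does not exceed 5%.

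**5. Power under each rule.** Completers = 0.85N; m = completers/18; noncentrality = 0.53 × √[completers/(4 × IF)].
- N = 140: 119 completers, m = 6.61, IF = 1.056, noncentrality 2.813.
- N = 148: 125.8 completers, m = 6.99, IF = 1.060, noncentrality 2.887.

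Individual-level degrees of freedom (df) are 117 and 124. The between-visitor value is 18 − 2 = 16. Ranges are for correlation 0 to 0.3.

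| Rule | N=148, individual df | N=148, 16 df | N=140, individual df | N=140, 16 df |
|---|---|---|---|---|
| One outcome at 0.05 | 82% | 77% | 80% | 75% |
| Both required, 0.53 SD on both | 67–69% | 60–62% | 63–66% | 57–59% |
| Holm, per outcome, 0.53 SD on both | 79% | 73–74% | 76–77% | 71% |
| Holm, per outcome, no effect on the other | about 73% | about 66% | about 71% | about 64% |

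The last row is the power at the 0.025 step. It applies only when the other outcome has no effect, because Holm tests the second outcome at 0.05 once the first has passed.

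**The case against.** **On time.** The only sentence defining the endpoint says 12 months, 3.2 and 8.2 agree, and 8.1 states an aim. In 8.3 and 8.3.2 the two times are attached to values to be calculated and summarised. This stands in part: the intended primary time is clear, and presenting 6 months as primary would contradict three places. But 8.1 and 8.3.2 carry the primary-endpoint label and should not leave both times unranked. A reader might go further and count four primary tests (two people, two times). The definition of the endpoint does not support that.

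**On clustering.** Section 8.3.1 names the mixed model specifically for primary and secondary outcomes, while the t-test sentence is general. This also largely stands. A reader might infer that the primary analysis ignores clustering; it does not. What remains is an unlabelled second set of tests, with small consequence at ICC 0.01, and an unclustered comparison of adverse events.

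**On two hypotheses.** The synopsis names caregiver and child weight as one endpoint, which may mean that both are required. Alternatively, 1a and 1b could be reported as separate claims about different people, where the need for joint error control is debated. Accordingly, an inflated error rate is not established: it would follow only from an either-counts rule that the documents nowhere state. The absence of any rule is established.

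**Conclusion.** The point holds as a correction of wording and decision rules. It does not show that the planned analysis is invalid.

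- **Time:** 8.1, 8.3 and 8.3.2 need aligning with the 12-month endpoint that the rest of the plan supports.
- **Unclustered tests:** a minor matter at the plan's ICC. The 8.6% figure rests on an assumed ICC five times larger.
- **Success rule:** the most consequential of the three. The overall error rate is 9.1–9.8% if either outcome suffices and not above 5% if both are required; in the second case power falls well short of 80%. These figures depend on the assumed correlations and, for power, on 0.53 SD for both mother and child, although 8.2 does not say to whom its 0.53 SD applies.

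The change should be made before analysis. Confidence is medium, because the size of the effect depends on a rule that is not written down.

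**What to change.** 1. In 8.1, 8.3 and 8.3.2, make the 12-month comparisons primary and the 6-month comparisons secondary. This is wording only.
2. In 8.3 and 8.3.1, state that the home-visitor mixed model is the only inferential test of primary and secondary outcomes, and label the unclustered t-tests and chi-square tests of outcomes descriptive. In 8.3.4, report adverse events descriptively or with a cluster-adjusted comparison. The mixed model is already planned, so no visits or data are added. No particular df method is recommended here; that is a separate question.
3. Replace the per-test 0.05 rule for 1a and 1b with a rule fixed before analysis. If the sponsor can say which of mother and child comes first, a fixed order keeps the full 0.05 and loses no power for that outcome; the second is tested only if the first succeeds. If neither comes first, use Holm. With 0.53 SD on both, Holm costs about 2–5 points per outcome compared with an unadjusted 0.05. If the other outcome has no effect, power is about 71–73% with individual-level df or 64–66% with 16 df. If the sponsor means both to be required, say so and state the joint power.
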